	Address of Institution		[name]											
	Web Site		http://											
	Tel. no. (office)		[name]			Fax no.								
	Tel no. (home)					Cellular [contact]						
	Email		[contact]											
Board Certification (for MDs only)	Which specialty(ies)?													
Relationship to P.I. (supervisor, associate investigator, student, etc.)	Student													
Scientific Interest (Key words)	Telepsychiatry													
Role in the project	Co-investigator													

2. Information on Associated Investigator No. 2 *

	Last name		First name	ID # (9 digits)									
	[name]	[name]	
Academic affiliation	University**		Hebrew University										
	Department or Faculty		Psychiatry, Faculty of Medicine										
	Rank		-										
†Current Employment	Position		General Medical Manager										
	Department		Pyschiatry										
	Name of Institution		Jerusalem Mental Health Center										
	Address of Institution		[name]										

	Web Site	http://		
	Tel. no. (office)	[name]	Fax no.	
	Tel no. (home)		Cellular phone no.	
	Email	[contact]		
Board Certification (for MDs only)	Which specialty(ies)?	Psychiatry		
Relationship to P.I. (supervisor, associate investigator, student, etc.)	Associate investigator			
Scientific Interest (Key words)	Military psychiatry, Epidemiology, Suicide, Schizophrenia			
Role in the project	Co-investigator			

A. English Abstract

Scientific Background: Patients with an acute psychiatric disorder and an indication for involuntary admission are legally required to be examined by a senior psychiatrist. Waiting in the emergency room, until the senior psychiatrist arrives, can be dangerous due to the aggravation of their mental state. In a previous study, we showed that remote video examination is effective and valid compared to face-to-face examination. This strategy has not yet been implemented in practice.

Objectives: 1. Implementation of tele-psychiatry for admission decisions in the emergency department (ED). 2. Implementation of tele-psychiatry prior to being brought to the ED. 3. Evaluation of the effect of these strategies on clinical outcomes and ED utilization.

Working Hypotheses: 1. Remote video psychiatric examination is safe and effective, compared to usual practice. 2. Implementation of telepsychiatry is feasible within the current context, infrastructure, and resources.

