Type of Research: Implementation of a novel strategy and comparison with historical controls.

Methods of Data Collection: In the first stage, we will implement remote interviews by senior psychiatrists in the ED, replacing face-to-face interviews. We will measure time spent in the ED, number of violent incidents, and duration of hospitalization. In the second stage, we will implement remote triage by a senior psychiatrist prior to transport to the ED. Patients may be directly admitted, remain at home, or be transported to the ED for further evaluation, based on the findings of the remote examination. At each stage of the study, patient outcomes ($n = 60$) will be examined over three months and compared to the three months prior to the study ($n = 60$).

Methods of Data Analysis: We will confirm that groups (pre- and post-implementation) are balanced on measured variables. Assuming they are, we will compare continuous variables (e.g., ED time) using t-tests, and categorical variables using chi-square tests.

Uniqueness or Special Relevance to the National Health Insurance Law: This innovative approach, supported by our preliminary research, has not been tried before. This study has the potential to lead to a system of care that is quite different from current practice and could improve patient safety and well-being.

Possible Policy Recommendations: If our study proves that a remote psychiatric examination is feasible, safe and effective, this approach may be incorporated into official policy. Patients would be able to have an expert, accurate, reliable and fast psychiatrist examination, in the ED or at home. Patients who do not need emergency hospitalization would not be forcibly brought for examination in the ED. Patients who need emergency hospitalization would be able to go directly and safely to an appropriate inpatient ward.

1. Scientific background:

a. *For Patients with Psychiatric Emergencies, The Emergency Department Is an Unsafe Environment*

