Independent Variables (The Intervention)

In each study phase, the independent variable will be the study intervention, which will be organized by time. Patients in the pre-intervention period (3 months) will be managed under usual care, and will be the comparison group. Patients in the post-intervention period (3 months) will be managed using the study intervention, and will be the “intervention” group.

Usual care is that patients with psychiatric emergencies are evaluated face-to-face in the ED by a senior psychiatrist for possible involuntary admission. The intervention is that this evaluation will take place via video-link.

Dependent Variables

Dependent Variables

Variable	Type	Data Collection Method
Interobserver Variability	Binary	All video interviews will be recorded. A second senior psychiatrist, blinded to the admission decision, will determine whether admission was warranted based on the recording.
Reversal of Admission	Binary	An involuntary admission which is reversed within 24 hours implies an unnecessary admission. The proportion of admissions reversed within 24 hours will be measured.
Emergency Room Length of Stay	Continuous (minutes)	Measured from the time of arrival in the ED until the patient physically leaves the ED – to go home or to go to the psychiatry ward. Already collected as part of routine practice.
Time from ED arrival to assessment	Continuous (minutes)	We will measure this ourselves, starting with the pre-intervention period. We will measure time until the senior psychiatrist begins his/her face-to-face or virtual assessment.
Violent Incidents in the ED	Binary (any/none)	As recorded by ED staff and adjudicated by blinded review of the chart by a senior psychiatrist.
Patient satisfaction with ED course	Ordinal	We will ask patients to rate their overall satisfaction with their stay in the ED, from 1-5 (very dissatisfied – very satisfied), as they are leaving – starting with the pre-intervention period.
Staff satisfaction with ED flow	Ordinal	We will ask physicians, nurses, and other staff to rate their overall assessment of ED flow, from 1-5, at the end of each month
Duration of hospitalization	Continuous	From the time of entering the ward until the time of leaving the hospital, in hours

Statistical Analyses

We will be comparing the pre-intervention period with the post-intervention period. Above, we have outlined the dependent variables for each phase, and how we will collect them.

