It is possible that for some outcomes, our study will suggest the absence of a harm from the novel strategy, but will not be definitive, and that a larger study may be required in the future. However, this concept (triage via tele-psychiatry) is currently not part of standard practice, and even a relatively small feasibility study, powered to exclude important harms, would be an important step forward.

Collection of Implementation Data

We propose to conduct this study as a hybrid implementation study, Type 1. Hybrid implementation studies aim to shorten the process of translating clinical innovations into practice by simultaneously collecting data about the **effectiveness** of the intervention about the **process** of implementing it.¹⁰ A Type 1 hybrid study primarily emphasizes the collection of effectiveness data, but also includes data collection about the implementation process. If the innovation is found to improve care, as we anticipate it will be, collecting data about the implementation process can help inform future efforts to scale up and spread the innovation to other centers (across Israel, and potentially outside it).¹⁰ To this end, we will interview staff who had a role in implementing the intervention in Phase 1 at the conclusion of Phase 1, when their memories of the implementation process are still fresh. At the conclusion of Phase 2, we will do the same. We will interview staff at various levels of the organization, including senior physicians, junior physicians, nurses, other medical staff, and administrators. Some staff members may be interviewed about both phases. Questions will relate to what went well or badly about the implementation process, what factors facilitated or acted as barriers to implementation, and what advice the respondent would give to someone implementing a similar program elsewhere. We will aim to interview at least 12 individuals total for each phase, since this number is usually sufficient to capture the full range of views on a subject.¹¹ Interviewees will provide consent to be interviewed and to record the interview; those who do not wish to consent will not be included in our study. Interview recordings will be thematically analyzed by our team and will be the subject of a separate report. Participants will not be identified by name in the report.

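### Stage 2 is compared only with pre-study usual care, so if ED video continues into Stage 2 the plan cannot show what pre-transport triage adds

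*Combined protocol and SAP*

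**What the plan says.** The abstract (Methods of Data Collection) describes two steps: "In the first stage, we will implement remote interviews by senior psychiatrists in the ED, replacing face-to-face interviews", and then "In the second stage, we will implement remote triage by a senior psychiatrist prior to transport to the ED". Under the second step, "Patients may be directly admitted, remain at home, or be transported to the ED for further evaluation". One comparator serves both: outcomes at each stage "will be examined over three months and compared to the three months prior to the study".

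Section 4, Independent Variables, says the same. "In each study phase, the independent variable will be the study intervention, which will be organized by time", and "Patients in the pre-intervention period (3 months) will be managed under usual care, and will be the comparison group". Statistical Analyses plans pre-versus-post tests only. It contains no Stage 2 versus Stage 1 contrast and no adjustment for time trend.

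The abstract treats triage as an aim in its own right. Its objectives include "2. Implementation of tele-psychiatry prior to being brought to the ED. 3. Evaluation of the effect of these strategies on clinical outcomes and ED utilization". Its Possible Policy Recommendations include conclusions specific to triage: some patients would no longer be brought to the ED against their will, and others would go straight to a ward.

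The body is less clear that Stage 2 exists. Section 2 lists only ED tele-psychiatry, section 4 (Patient Population) counts one three-month study period, and Independent Variables defines one intervention, the ED evaluation by video-link. Yet Collection of Implementation Data still schedules staff interviews after each phase: "At the conclusion of Phase 2, we will do the same".

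**The concern.** By the time Stage 2 starts, the ED has already changed from face-to-face to video interviewing, and no return to the old procedure is described. If video stays in place, the difference between Stage 2 and the pre-study months has several sources: the switch to ED video, the staff's accumulated experience with it, at least one further three-month stage of calendar time, and pre-transport triage. No planned comparison separates the last of these from the rest.

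This matters because triage before transport is the larger change in policy. A favourable Stage 2 result would be read as support for it even if the whole gain came from ED video. Stage 1's own comparison with the pre-study months is not affected.

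**Working it through.** **Inputs** (section 4, Statistical Analyses and Justification of Sample Size): mean ED time 3 h; ±1 h, read here as the SD; Phase 1 reduction 1 h; 60 patients per period; unpaired t-test, two-sided 0.05.

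**The plan's own figure.** The plan states 80% power for Phase 1.
- Standard error of the difference = SD × √(2/n) = 1 × √(2/60) = 0.1826 h.
- Power ≈ Φ(1/0.1826 − 1.960) = Φ(5.477 − 1.960) = Φ(3.517) = 0.9998. The noncentral t gives 0.9997.

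The 80% does not reproduce. With 60 per group, 80% power goes with a difference of (1.960 + 0.842) × 0.1826 = 0.51 h, or with a 1 h difference and an SD of 1/0.5115 = 1.96 h. That discrepancy is a separate matter, but it is why the larger SD is also carried below.

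**Stage 2 versus pre-study when triage adds nothing.** Let *c* be the part of the Stage 1 reduction that persists into Stage 2. The expected difference is then *c*, and the chance of a significant result is about Φ(*c*/0.1826 − 1.960).

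| *c* (h) | *c*/0.1826 | Normal approximation | Noncentral t |
|---|---|---|---|
| 1.00 | 5.477 | 0.9998 | 0.9997 |
| 0.75 | 4.108 | 0.984 | 0.983 |
| 0.50 | 2.739 | 0.782 | 0.775 |
| 0.25 | 1.369 | 0.277 | 0.274 |

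With SD 1.96 h and *c* = 1 h, the standard error is 1.955 × 0.1826 = 0.357 h, and the probability is Φ(2.802 − 1.960) = about 0.80.

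The third row has a second reading. If the full hour persists and Stage 2 lengthens ED time by 0.5 h relative to Stage 1, the net difference from pre-study is 0.5 h. Stage 2 would still be significantly better than pre-study about 78% of the time.

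**Stage 2 versus Stage 1.** With full persistence, no learning and no trend, the expected difference is zero and the test is significant about 5% of the time (5.2% in 50,000 simulated studies, SD 1 h).

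This contrast has limits of its own:
- If staff learning or calendar change alone shortened ED time by 0.25 or 0.5 h (an assumed range), the same arithmetic gives a significant result about 27% or 78% of the time with triage contributing nothing.
- At 60 per stage and SD 1 h, 80% power is reached only for a further reduction of 0.51 h (0.5115 × 60 = 31 minutes). From n = 2 × (1.960 + 0.842)² / d², further reductions of 1, 0.75, 0.5 and 0.25 h need 16, 28, 63 and 252 per stage.

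The illustration covers ED time only. The documents give no rates for violence or for reversal of admission. It also treats ED time as defined for everyone, which Stage 2 would break: patients who stay at home or are admitted directly have no ED stay.

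**The case against.** The strongest reply is that usual care is the right comparator for the hypothesis as written, which sets remote examination against usual practice. The design is declared as a comparison with historical controls, and the objective of evaluating the strategies does not expressly promise an increment over ED video. This stands. Stage 2 versus pre-study is a meaningful contrast for the whole package, and a reader who infers that it is invalid goes too far. It does not answer a question about triage alone, and the abstract draws conclusions about triage alone.

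Second, continuation of ED video in Stage 2 is inferred. A reader might take it as established from the Patient Population text, which calls the change one that lasts as long as the study. That sentence justifies the consent waiver, and the same section sets the study at three months, so it does not settle what happens in a later stage. No text says how Stage 2 patients who reach the ED are interviewed. If ED video were withdrawn, the carry-over would shrink.

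Third, Stage 2 is defined only in the abstract. The disagreement between abstract and body over whether it is part of the study comes before any choice of comparator. This also stands, and the fix begins there.

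Fourth, the 99.97% figure is Stage 1's own power, obtained by assuming full persistence, a one-hour effect and zero benefit from triage. It is the extreme of a range and should not be read as the trial's false-positive rate.

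Finally, a reader might infer that testing Stage 2 against Stage 1 isolates triage. It does not, because learning and calendar change remain in that contrast.

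**Conclusion.** The concern holds in a conditional form. If Stage 2 is run and ED video continues through it, the only planned Stage 2 comparison estimates the combined effect of both changes, and no claim for pre-transport triage can rest on it. On the plan's ED-time figures, a Stage 2 that adds nothing would be significant versus pre-study with probability about 99.97%, 98%, 78% or 27% as the persisting Stage 1 effect goes from 1 h down to 0.25 h in quarter-hour steps (SD 1 h). For the full hour the figure is about 80% at SD 1.96 h.

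These figures assume a common mean shift, 60 patients per period, and ED time defined for all patients. They show how readily a carried-over effect would pass as a Stage 2 benefit. They do not predict that triage is without value, and they do not undermine the package comparison or Stage 1's own comparison.

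**What to change.** 1. Reconcile the abstract with sections 2 and 4 on whether Stage 2 is part of the study.
2. If it is, state how Stage 2 patients brought to the ED are interviewed.
3. Label Stage 2 versus pre-study as the combined effect of ED video and triage.
4. Add Stage 2 versus Stage 1 as the contrast on which any claim for triage must rest. Use one referral-based case definition in every period (all patients needing an involuntary-admission decision) and outcomes defined without an ED visit. The present entry criterion, needing an ED interview, would drop the patients whom triage diverts. Four of the eight listed outcomes (ED length of stay, time from ED arrival to assessment, violence in the ED, and patient satisfaction with the ED course) exist only for patients who reach the ED.
5. State the limits of that contrast: learning and calendar change remain in it, and 60 per stage gives 80% power only for about 0.51 h at SD 1 h.
6. If Stage 2 is not run, remove objective 2 and the Phase 2 text, and make no claim for pre-transport triage.

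**Cost.** The labelling and the added contrast are changes of wording, and Stage 1 data are collected anyway. The referral-based definition and the new outcomes are real work. They are best fixed before the pre-study months begin, because some outcomes are collected specially from that period on. The incremental estimate may be smaller than the package estimate and less likely to reach significance.

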In Israel, it is the law that before a patient can be hospitalized involuntarily, he must be evaluated in-person by a senior psychiatrist. The intent of this longstanding policy is to ensure a thorough evaluation before taking the relatively audacious step of hospitalizing a patient involuntarily. However, this policy was created before it was possible to evaluate a patient by video-link. Medical care is increasingly possible via video-link,⁵ but Israel's policy of requiring an in-person evaluation by the senior psychiatrist remains in place. Because the senior psychiatrist is often at home, and not already in the hospital, this policy causes the patient to wait in the ED until the psychiatrist arrives. This additional waiting time can increase the opportunities for the

Protocol Name: Telepsychiatry Emergency; Version: 1.0; Date Nov 5, 2021
patient to decompensate. We will implement evaluation for involuntary admission via video-link, and measure the impact on patient outcomes.

Our study is premised on the idea that reducing friction for patients with psychiatric emergencies, and reducing irritation when they are least equipped to handle it, will lead to reduced opportunities for decompensation and clinical deterioration.² We expect to show that psychiatric ED visits can be shortened, and in many cases, obviated entirely. We expect to show that this approach increases patient safety and promotes quicker resolution of the underlying psychiatric issue.

Many clinical protocols, including those in psychiatry, exist because they have always been done that way, and have never been challenged.⁶ These protocols may have developed by chance, or because it was convenient for physicians, or because of the way hospitals functioned 100 years ago. It is important to reimagine those aspects of medical care that do not have to remain they way they have always been, because they may represent opportunities to improve patient outcomes.⁶

b. Our Group Has Demonstrated that Remote Psychiatric Triage Is Feasible and Valid

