The arguments in favor of virtual triage in the ED are much stronger. We expect that this change will reduce risk to patients, and risk to others, from violent outbursts. We expect that both phases will reduce patient discomfort, distress, and fear. Lessening decompensation by patients in the ED will allow therapeutic strategies to commence earlier, contributing to earlier recovery and earlier hospital discharge.

It is worth noting that our project is defensible on the basis of benefit to patients alone (otherwise, we would not consider it). There are other likely benefits, which do not enter directly into our calculus. This project is likely to reduce ED crowding. Also, this project will save the attending psychiatrist the need to travel to the hospital for most evaluations. We emphatically repeat that while these are indeed benefits, they are not the basis for us performing the study, nor would they be a sufficient reason for this change in policy.

2. Objectives

- i. We will implement tele-psychiatry evaluations in the ED.
- ii. We will evaluate the impact of this strategy on patient outcomes and healthcare utilization, compared to historical controls.

3. Working Hypotheses

- a. Remote video psychiatric examination is safe and effective, as measured by clinical outcomes, when compared to usual practice. Patients will spend fewer minutes in the ED, compared with historical controls. There will be fewer violent incidents in the ED. There will not be an increase in the frequency of reversal of involuntary hospitalization, which would imply that a patient was needlessly admitted.
- b. Implementation of telepsychiatry will be feasible within the current context, infrastructure, and resources.

4. Comprehensive description of study design and methodology:

Patient Population

We will recruit study participants from the Jerusalem Mental Health Center, located at Kfar Shaul and Ichilov Medical Center. We will obtain a waiver of informed consent, as this will be a change in standard procedure for all patients for the duration of the study.

We will include all patients who require an ED interview and an involuntary admission decision by a senior psychiatrist. We will compare patients from the three months prior to the study (approximately 60, based on usual rates of admissions) with patients from the three months of the study (also 60).

The absence of exclusion criteria will ensure that the study results will be broadly generalizable.

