We will start by comparing the pre- and post-groups on important baseline characteristics. These will include age, sex, ethnic/social group (Haredi, Arab, General Population), socioeconomic status, and underlying condition (schizophrenia, bipolar disorder, other). We will compare these variables between pre- and post-groups using appropriate bivariate tests (t-test, chi-square). If we find a statistically significant imbalance ($p < 0.05$), we will utilize a multivariable analysis in the main analysis to correct for the imbalanced factors. We do not propose to control for all potential covariates because of limited sample size.

In the main analysis, we will compare the dependent variables explained above between the pre- and post-periods. For continuous variables, we will use an unpaired t-test. For categorical variables, we will use a chi-square test. We will perform two-tailed tests, and will consider $p < 0.05$ to be statistically significant. In the event that we have detected an important between-group imbalance, we will use an appropriate regression model (logistic or generalized linear model), controlling for only the factors that have been found to be unbalanced.

Potential Sources of Bias

A sample size of 60 each in the pre- and post-intervention groups will make it unlikely, but not impossible, that random chance will lead to important between-group imbalance on measured factors. We will assess for such imbalance as part of the analysis plan, as noted above. If there are important differences, we will conduct multivariable analyses to control for a limited number of important unbalanced covariates.

Justification of Sample Size and Study Duration

The study duration is dictated by the maximal duration of a study funded by Machon HaLeumi. The sample size is dictated by the approximate number of patients admitted to our center each month. With 60 patients in the pre-intervention period and 60 in the post-intervention period, we will have statistical power to show a large effect size for some variables, and a moderate effect size for others. For example, if we assume that the average time in the ED is currently

3 ± 1 hours, and that the Phase 1 intervention will reduce this time by one hour, with 60 patients in each group, we would have 80% power to detect such a difference.

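### Arrival shift is likely to predict the ED time outcomes strongly, by the protocol's own reasoning, yet it is neither compared between the two periods nor adjusted for

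*Combined protocol and SAP*

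**What the plan says.** - **Mechanism.** Section 1a attributes the wait to the in-person rule: "Because the senior psychiatrist is often at home, and not already in the hospital, this policy causes the patient to wait in the ED". Section 1c says that "this project will save the attending psychiatrist the need to travel to the hospital for most evaluations". Both statements allow for evaluations that need no travel.
- **Population.** Under Patient Population, "We will include all patients who require an ED interview and an involuntary admission decision by a senior psychiatrist". There are no exclusions, on the ground that "The absence of exclusion criteria will ensure that the study results will be broadly generalizable". The three months before the study are compared with the three study months, about 60 patients each.
- **Balance check.** Under Statistical Analyses, the factors are listed as follows: "These will include age, sex, ethnic/social group (Haredi, Arab, General Population), socioeconomic status, and underlying condition". All five describe the patient. None records the hour or day of arrival, or where the senior psychiatrist was.
- **Main analysis.** "For continuous variables, we will use an unpaired t-test". Regression is used only if a listed factor differs at p<0.05, "controlling for only the factors that have been found to be unbalanced".
- **Bias.** Potential Sources of Bias discusses only random imbalance on measured factors.
- **Data at hand.** The Dependent Variables table measures ED length of stay from arrival, as part of routine practice. Time from arrival to senior assessment is measured by the team in both periods.

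**The concern.** The controls are historical: one quarter is set against the quarter before it. In such a design, a strong predictor of the outcome whose distribution changes between the quarters produces a difference that has nothing to do with the intervention. The protocol's own account of the delay points to such a predictor. If the wait comes largely from a psychiatrist travelling in, patients who arrive when nobody senior is on site should wait longer under usual care than those who arrive when one is.

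The plan would neither show a difference in shift mix nor correct for it, because a factor that is never examined cannot be found unbalanced. More night, weekend or holiday arrivals in the earlier quarter would flatter video. More of them in the later quarter would hide a benefit. Time in the ED leads the list of expected benefits in the Working Hypotheses and is the example used to justify the sample size, so it should be protected against this explanation.

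**Working it through.** **Inputs from the documents.** 60 patients per period; two-sided p<0.05; ED time 3 ± 1 hours, with the ± 1 read as an SD of 1 h; a reduction of 1 h; stated power 80%.

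**Assumed, because the documents give no figure.** A usual-care gap of 60 minutes in mean ED time between shifts; differences in shift mix between quarters of 10 and 20 percentage points; off-site shares of 50% to 80%.

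**1. The plan's own figure.** The standard error of the difference is 1 h × √(2/60) = 0.183 h, about 11 minutes. Power for a 1 h reduction is then 99.98%, not 80%. With 60 per period, 80% power corresponds to a difference of about 0.51 h. This mismatch is a separate matter and does not decide the present point, but step 5 uses the same inputs.

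**2. Bias from a systematic mix difference, with no effect of video.** Bias = gap × difference in shift share.

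| Gap | Mix difference | Bias | Bias ÷ SE | Chance of p<0.05 |
|---|---|---|---|---|
| 60 min | 0 points | 0 min | 0 | 5% |
| 60 min | 10 points | 0.10 × 60 = 6 min | 0.1/0.183 = 0.55 | 8.5% |
| 60 min | 20 points | 0.20 × 60 = 12 min | 0.2/0.183 = 1.10 | 19.5% |

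Against the planned 60-minute reduction, these biases are 6/60 = 10% and 12/60 = 20%.

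**3. Would adding shift to the balance screen be enough?** With a share near 50%, the standard error of the difference in share is √(2 × 0.25/60) = 0.091. A difference must reach 1.96 × 0.091 = 0.18, about 18 points, before it is significant. The 10-point case would usually pass the screen and stay unadjusted.

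**4. Gain in precision.** With a 60-minute gap and a total variance of 1 h², shift accounts for s(1 − s) of the usual-care variance, where s is the on-site share: 0.2 × 0.8 = 16% at s = 20%, and 0.4 × 0.6 = 24% at s = 40%. A covariate would remove that part from the residual.

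**5. Is power at risk from pooling?** Suppose 60 minutes are saved for off-site arrivals only. The pooled effect is 60 × off-site share, with SD 1 h and 60 per period.

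| Off-site share | Pooled effect | Power |
|---|---|---|
| 80% | 48 min | 99% |
| 60% | 36 min | 91% |
| 52% | 31 min | 81% |
| 50% | 30 min | 78% |

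**The case against.** **The all-patient mean is the question asked.** A reader might infer that pooling answers the wrong question. It does not. The Working Hypotheses state that patients will spend less time in the ED than historical controls, and the population is deliberately unrestricted. The all-patient difference is the effect of the policy. This objection stands.

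**Pooling does not clearly dilute a planned effect.** A reader might infer that a real off-site benefit would be missed. The sample size section assumes that average ED time falls by an hour, which reads as an average over all patients. On that reading, off-site savings would be 60/0.8 = 75 or 60/0.6 = 100 minutes at off-site shares of 80% or 60%, and nothing is lost. On the less favourable reading in step 5, power stays near or above 80% at the off-site shares above half that section 1c implies. This objection also stands.

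**The wait may not be confined to off-site hours.** Section 1a says that the psychiatrist is often at home. It does not say that one who is on site is free at once, or that video saves nothing then.

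**Chance imbalance is already covered.** Differences between shifts are part of the SD, so the t-test's standard error allows for random variation in mix. A 10-point difference is about one standard error of the difference in share. Only a systematic change biases the comparison, and the documents give no specific reason to expect one.

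**The plan partly addresses the point.** Time to assessment targets the wait directly, and the list of factors is worded loosely enough to allow additions. But time to assessment is itself compared between the same two quarters and is open to the same shift mix, and no shift factor is named.

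What survives is that a systematic change in mix would be invisible and uncorrected under the plan as written.

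**Conclusion.** The point holds as a gap in confounder control, and the improvement is cheap. By the protocol's own reasoning, arrival shift is likely to be a strong predictor of ED length of stay and time to assessment, yet it is neither compared nor adjusted for. Under an assumed 60-minute gap, mix differences of 10 and 20 points give spurious effects of 6 and 12 minutes and raise the false-positive rate from 5% to 8.5% and 19.5%, with SD 1 h and 60 per period. The gap, the mix difference and the direction are all unknown.

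The documents do not support going further. They do not show that the wait arises exclusively when the psychiatrist is away, that the pooled comparison is invalid or underpowered, or that the shift mix did change.

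**What to change.** 1. Derive arrival shift for every patient in both periods (regular hours versus night, weekend or holiday) from the date and time of ED arrival. Where a duty roster or a prospective record allows it, use senior psychiatrist on site versus off site instead. The documents mention no roster, so the shift version should be the default.
2. Report the shift mix in each period beside the five existing factors.
3. Always include shift as a covariate in the models for ED length of stay and time to assessment, whatever the p<0.05 screen shows.
4. Keep the all-patient estimate as the main result. Pre-specify an off-hours (or off-site) estimate as a secondary analysis of the proposed mechanism. Define it before outcomes are examined, because a subgroup chosen afterwards would carry little weight.

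**Cost.** One derived variable, one model term and a few sentences of analysis text. The secondary estimate rests on fewer than 60 patients per period, so it must be read with that smaller sample in mind. Clock time is only a proxy for where the psychiatrist was, so some confounding may remain.
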